7.1.2019

**Double blind Study – Use of Gelronate Gel vs. Aloevera in Preventing /  
Minimizing Radiation-Induced Dermatitis in Breast Cancer Patients****Principle Investigator:** [name], Head, Breast Radiation unit,  
Sheba Medical Center**Study Number:** 5652-18-SMC**Aim:** To evaluate the effect of Gelronate® gel, NaHA based product (medical device for topical application) vs. Aloevera Jell, in preventing or minimizing of radiation induced skin reaction in breast cancer patients.**End Points:**

1. Primary – Development and degree of any skin reaction.
  - a. Grading according to RTOG skin toxicity score (appendix1).
  - b. Assessment of skin reaction by scoring of weekly digital photographs.
  - c. Patient comfort assessed by weekly administrated questionnaire.
2. Secondary – Skin reaction requiring conventional topical therapy (e.g. steroid cream etc.) as evaluated by clinical judgment of radiotherapy nurse/ radiation oncologist at OTV (on treatment view visits).

[figure not shown]

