### Study Plan

120 female patients planned to receive whole breast radiation (+/- lymphatic drainage) in the radiotherapy unit at Sheba, who give written consent for participation, will be entered into the study and randomized. Based on statistical evaluation, 65 will receive the aloe Vera and 55 will receive the HA Gelronate® in blinded packages.

Patients will undergo CT simulation with 3D treatment planning (as routinely done) and will receive 42.4 Gy in daily fraction of 2.65 Gy, five times per week to the whole breast according to the standard department protocol, with or without concomitant or subsequent lumpectomy cavity boost. Patient data including demographics, staging, systemic therapy, radiation details, other medications will be recorded in the attached forms (Appendix A, pages 7-9 below).

BTG will provide sets of bottles sufficient for treatment of at least 120 patients, plus any extra gel bottles as needed for the participants to complete accrual and full treatment for 120 patients.

The study nurses will provide each patient with the bottle and will ensure that the patient understands how to apply according to protocol. The gel will be applied as a thin lotion twice a day, immediately after radiotherapy treatment and once more in the evening/morning. The therapy should continue for 10 days following the end of radiation therapy.

The study nurses will examine each patient weekly during treatment and 7-10 days after completion of radiotherapy. At each visit skin reaction based on RTOG toxicity score will be recorded and the patient will complete a short questionnaire regarding subjective and objective skin reaction. The patient's skin will be photographed (no face in the picture) on fraction 10-11, 15-16 and at the follow-up visit, days 9-10 after the end of radiation. This will be done with a digital camera and the electronic image will be stored for later evaluation. The images will be stored anonymously except for the patient's study number.

Any patient developing moist desquamation or other grade 3 skin reaction during the radiation will stop treatment and will receive topical therapy as clinically indicated.

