**Statistical Considerations:**

Based on published data and previous experience we expect around 90% of patients to develop some degree of skin reaction and about 20% would require medical intervention due to grade 2-3 skin reactions. (Ben-David et al 2016, Fenig et al., Kodiyan et al. 2015, Olsen et al 2001).

The relative large number of patients in the study was chosen in order to be able to have sufficient amount of data on large variety of patients (different age, BMI, skin color, origin, smokers/non-smokers etc.). Participation in this study will be offered and available to all radiation treated patient in the institute, therefore large variety of patients are expected to participate in this study. As a result, the data that will be obtained in the study may be used by any irradiation institute in the world.

In addition to the weekly nurse/patient evaluation of skin toxicity (see appendix A), at the completion of the study the patient photographs will be evaluated blindly by a panel of 3 radiotherapy staff. The digital photo with the worst reaction of each patient will be scored.

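### The secondary endpoint is judged at on-treatment visits, so a need for topical therapy first arising afterwards, while gel use and follow-up continue, is not counted

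*Protocol*

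**What the plan says.** Under End Points, the secondary endpoint is the need for conventional topical treatment of a skin reaction, "as evaluated by clinical judgment of radiotherapy nurse/ radiation oncologist at OTV (on treatment view visits". The protocol spells out the abbreviation OTV itself and names no other occasion for this judgment.

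The Study Plan describes a longer period of treatment and observation. On gel use: "The therapy should continue for 10 days following the end of radiation therapy". On visits: "The study nurses will examine each patient weekly during treatment and 7-10 days after completion of radiotherapy". On what is collected: "At each visit skin reaction based on RTOG toxicity score will be recorded", together with a patient questionnaire. A photograph is also taken "at the follow-up visit, days 9-10 after the end of radiation".

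Statistical Considerations gives the only expected frequency for this kind of event: "about 20% would require medical intervention due to grade 2-3 skin reactions". It does not say over what period.

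**The concern.** The protocol treats and assesses patients after radiation, but the secondary endpoint as worded stops at the on-treatment visits. Consider a woman who first needs a steroid cream a few days after her last fraction, while still applying study gel. She can be recorded with a worse RTOG grade at follow-up and still have no secondary event. The Aim, to prevent or minimise the reaction, carries no such time limit.

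Two things are at stake. The first is undercounting: any late need is lost, in either arm, from an endpoint expected in only a minority of patients. The second is conditional: if one gel shifted the need to a later date without removing it, this endpoint would show a difference that a count through follow-up would not.

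This is not a detail left to the statistical analysis plan. The protocol names the assessment occasion, and names it more narrowly than its own visit schedule allows.

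**Working it through.** The point concerns a window, so the protocol has no calculated figure to reproduce.

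**Coverage of each measure (End Points and Study Plan)**

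| Measure | During radiation | Visit after radiation |
|---|---|---|
| RTOG grade (primary) | weekly | yes |
| Questionnaire (primary) | weekly | yes |
| Photograph (primary) | fractions 10-11 and 15-16 | yes |
| Need for topical treatment (secondary) | on-treatment visits | not named |

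**Share of gel days after radiation.** Input: "42.4 Gy in daily fraction of 2.65 Gy, five times per week", then 10 further days of gel.

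- Fractions: 42.4 / 2.65 = 16.
- Calendar span: 16 = 3 × 5 + 1, so three full weeks plus one day, 3 × 7 + 1 = 22 days, whatever the starting weekday.
- Gel period: 22 + 10 = 32 days.
- Share after radiation: 10 / 32 = 31%.

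Two things move this figure. A subsequent boost, which the Study Plan allows, lengthens radiation and lowers the share. In the other direction, the visits are weekly, so the last on-treatment visit may fall before the last fraction, and the stretch not covered can then exceed 10 days.

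**When the arms would be affected differently (illustration on assumed values).** Assume that the true need through follow-up is 20% in both arms, with 65 aloe vera and 55 Gelronate patients and a two-sided 5% test. Let f be the share of need that first arises after the last on-treatment visit. The on-treatment rate is then 20% × (1 − f).

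- f = 25% in both arms: 15% vs 15%, difference 0. Events are lost but no false difference arises.
- f = 0 for aloe vera and 25% for Gelronate: 20% vs 15%, an apparent benefit of 5 points; chance of a significant result about 10%.
- f = 0 for aloe vera and 50% for Gelronate: 20% vs 10%, an apparent benefit of 10 points; chance about 32%.
- Any f, with the follow-up visit counted: 20% vs 20%.

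The protocol gives no value of f for either arm. The one-sided cases show the mechanism and are not estimates.

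**The case against.** The protocol does not say that on-treatment visits are the only occasion. The phrase can be read as naming who judges and the usual setting. The Background words the purpose as reducing reactions during radiation, and the Study Plan's rule for moist desquamation or grade 3 reactions also refers to that period, so an on-treatment window may have been intended. The Study Plan has other medications recorded on forms, and the data collection CRF appears in the available text as a heading only, so topical treatment at follow-up may already be captured somewhere. Finally, the primary measures include the follow-up visit and would show a late reaction.

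Part of this stands. The restriction is an inference from naming one kind of visit and no other. The primary endpoint is not affected, and different windows for primary and secondary endpoints are not in themselves an error. But capturing a medication on a form does not make it an endpoint event, and no text brings a need first seen after radiation into this endpoint. An intended on-treatment window also fits poorly with 10 more days of gel and a scheduled examination. The primary measures record grade, appearance and comfort; they do not record whether treatment was needed.

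A reader might go further and infer that a merely postponed reaction is scored as prevented, to the advantage of one gel. The documents do not support that as a general statement. It could apply to the secondary endpoint only, and it favours one arm only if the gels differ in timing of onset.

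**Conclusion.** The point holds as a defect in the wording of the secondary endpoint. A first need for topical treatment after the last on-treatment visit is not counted, although patients are still using the gel and are examined again. Late events are lost in both arms; bias in the comparison is conditional on different timing between the gels.

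The size can be given in days only: about 10 of 32 gel days, assuming no subsequent boost. A reader might turn this into lost events: 20% of 120 is 24, and if 10-50% of needs arose late, about 2 to 12 would be missed. The protocol does not support that count. It gives no timing of need, and it does not say whether the expected 20% runs through follow-up. If the 20% is an on-treatment rate, none of those 24 is missed and any late events come on top. Nor can a loss of power be claimed, since the protocol states no power for this endpoint.

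The correction is worth making because it is cheap and removes an ambiguity that staff could otherwise resolve differently from patient to patient.

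**What to change.** Define the secondary endpoint as a skin reaction that the radiotherapy nurse or radiation oncologist judges to need conventional topical treatment at any visit from the first fraction through the existing follow-up visit 7-10 days after completion. At that visit, record any topical treatment started since the last on-treatment visit and have the same judgment made on it, so that the endpoint remains one of clinical judgment. Report the on-treatment count as a descriptive subset. If an on-treatment window was intended, the protocol should say so and give the reason.

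Cost: one sentence in End Points and one item on the form used at a visit that already takes place. No visits or patients are added. Since the Study Plan assigns that visit to the study nurses, the text should also make clear who makes the judgment there.

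Two downsides remain. Treatment started between visits is partly patient-reported. A visit held on day 7 leaves up to 10 − 7 = 3 gel days unobserved. The Study Plan places the follow-up photograph on days 9-10 but the examination on days 7-10; reconciling the two would settle how much of the gel period stays uncovered. No change in sample size follows from the documents.

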**Background**

One of the dose-limiting effect of radiotherapy is the acute reaction that ionizing radiation induces in normal tissues, i.e. skin. The severity of this acute reaction may link to different parameters, patient associated (BMI, diabetes) and radiation associated (dose per fraction and total dose).

Hyaluronic acid (HA) is linear polysaccharide formed from repetitions of a disaccharide unit composed of one aminosugar and one uronic acid residue ([D-glucuronic acid (1- $\beta$ -3) N-acetyl-D-glucosamine (1- $\beta$ -4)]n) (Figure 1).

Study Protocol V3 7.1.2019

Fig. 1. Disaccharide repeating unit of hyaluronic acid.

The biopolymer is widespread in soft tissues (vitreous humour of the eye, joints, synovial fluid, skin and more). In vertebrates, HA has a wide variety of functions including maintenance of tissue hydration in the skin, sustaining tissue physical properties and induce rate changes in cell proliferation, cell migration and angiogenesis.

There are two industrial methods for the production of HA: from rooster combs or from bacterial fermentation. Bio-Technology General (Israel) Ltd. developed and manufacture HA for ophthalmology and orthopedics purposes. BioLon and BioLon Prime are two products for operations in the interior chamber of the eye (cataract surgeries, cornea implantation etc.) and Euflexxa (Arthrease) syringes are for pain relief in patients suffers from osteoarthritis (OA).

Due to its characteristics and biological properties including wound healing (Primavera et al. 2006, Moore et al 2005, Hanci et al 2015), HA may eliminate or reduce adverse events (AEs) like skin dermatitis. The purpose of this study is to evaluate the capability of 1% HA solution to eliminate or reduce skin reaction during radiation i.e. dermatitis.

The tested product, Gelronate®, is gel composed of 1% high molecular weight pharmaceutical grade sodium hyaluronate and two types of commercial preservatives (Germal 115 and Phanochem/Salinip/Phenonip) dissolved in pharmaceutical grade purified water. Gelronate® supply in an airless pump bottle contain ~30ml gel. The aloe Vera 99.9% product is made by ESI, Israel, with no artificial coloring, in the same package with no identification.

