### **Eligibility:**

#### **Inclusion Criteria:**

1. Female patients aged at least 18 years with unilateral breast cancer following lumpectomy +/- chemotherapy.
2. Planned to receive 42.4 Gy whole breast irradiation +/- boost to tumor bed.
3. ECOG performance status 0-2.
4. Capable of giving written informed consent.
5. No co-morbidities known to affect radiotherapy reactions.
6. No co-existing acute or chronic skin disease.
7. No evidence of infection or inflammation of breast to be treated.

8. Not receiving chemotherapy during radiotherapy course. Biological therapy (e.g. Herceptin) or hormone therapy will be allowed during the study.

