**Exclusion Criteria:**

1. Chemotherapy within 4 weeks prior to planned start of radiation or chemotherapy planned during radiation.
2. Prior radiotherapy to the chest wall.
3. Collagen vascular disease.
4. Participation in other clinical study.

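### The eligibility criteria do not exclude women with a known allergy to an ingredient of either gel, although both gels are supplied unmarked

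*Protocol*

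**What the plan says.** **Products (Background).** The test gel holds 1% sodium hyaluronate and "two types of commercial preservatives (Germal 115 and Phanochem/Salinip/Phenonip) dissolved in pharmaceutical grade purified water". The comparator is a 99.9% aloe vera product supplied "in the same package with no identification".

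**Allocation and use (Study Plan).** Of 120 women, "65 will receive the aloe Vera and 55 will receive the HA Gelronate® in blinded packages". The gel goes on twice a day during radiotherapy and for 10 days afterwards.

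**Eligibility.** The inclusion criteria nearest to the point are numbers 5 to 7: "No co-morbidities known to affect radiotherapy reactions"; "No co-existing acute or chronic skin disease"; "No evidence of infection or inflammation of breast to be treated". The exclusion list opens with "Chemotherapy within 4 weeks prior to planned start of radiation or chemotherapy planned during radiation", continues with earlier chest-wall radiotherapy and collagen vascular disease, and closes with "Participation in other clinical study".

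**Outcomes (End Points, Appendix A).** The aim concerns skin reactions caused by radiation. The primary endpoint counts a skin reaction of any kind, graded by RTOG and supported by photographs and a questionnaire. The secondary endpoint is a reaction that needs conventional topical therapy.

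**The concern.** Blinding removes the safeguard that a woman with a known contact allergy normally uses, which is reading the label. The protocol therefore has to make that check for her before randomisation, and the written criteria do not. What is at stake is first her safety: repeated application of a known allergen to skin that is being irradiated.

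There is a smaller problem of interpretation. Erythema, swelling and peeling can come from the gel or from the radiation. If nothing in the scoring separates the two, a reaction to an ingredient enters the same grade as the radiation effect that the trial sets out to study.

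**Working it through.** The check is a reading of every criterion, followed by a short calculation of exposure.

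**1. All twelve criteria against a test case.** Take a woman with a documented contact allergy to one preservative in the test gel, clear skin at entry and no other relevant history.

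| Criteria | Subject | Does it stop her? |
|---|---|---|
| Inclusion 1–4 | sex, age and diagnosis; planned breast dose; performance status; consent | No |
| Inclusion 5 | co-morbidity that alters the response to radiotherapy | No: a product allergy is a different matter |
| Inclusion 6 | skin disease present alongside the cancer | No: her skin is clear, and a past sensitisation is not named |
| Inclusion 7 | current infection or inflammation of the breast | No |
| Inclusion 8 | chemotherapy during radiotherapy | No |
| Exclusion 1–4 | recent or planned chemotherapy; earlier chest-wall radiotherapy; collagen vascular disease; another study | No |

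She is eligible. The Statistical Considerations section adds that the study is offered to all women irradiated at the institute, so no narrower recruitment rule keeps her out.

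**2. Her chance of receiving the allergen.** The arms add up as stated: 65 + 55 = 120. At that allocation:

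- allergen only in the test gel: 55/120 = 46%;
- allergen only in the aloe vera gel: 65/120 = 54%;
- allergen in both: 100%.

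An eligible woman with a known allergy thus faces roughly an even chance or worse.

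**3. Length of exposure.** 42.4 Gy / 2.65 Gy = 16 fractions, given five per week, then 10 further days, with two applications a day unless treatment is stopped.

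**4. How a contact reaction would be scored.** In Appendix A, RTOG grades 1 and 2 are defined by appearance: erythema, desquamation, edema. The nurse checklist has separate lines for erythema, rash, swelling and peeling. No field or rule assigns a cause. The form does have a free-text clinical description and a weekly decision to continue or stop, so a suspicion can be written down and acted on. Neither changes the recorded grade.

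**5. Why no effect on event rates is calculated.** Let *s* be the share of women in one arm who react to an ingredient at the relevant grade, independently of their radiation reaction, and let *p* be the background rate. The arm's rate rises by *s*(1 − *p*). With the protocol's expected rates this is *s* × (1 − 0.90) = 0.1*s* for any reaction, and *s* × (1 − 0.20) = 0.8*s* for grade 2–3 reactions needing intervention. The protocol gives no value for *s*, nor for the part of *s* that is already known to the woman, which is the only part an exclusion could remove. The formula shows only that any shift is smaller than *s*, and much smaller for the endpoint of any reaction.

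**The case against.** **A reader might infer that the comparison between arms is biased.** The documents do not support that. Randomisation spreads sensitised women between the arms by chance, and the primary endpoint counts a reaction of any kind. If one gel provokes more reactions, that is in part a real effect of the product. A difference in sensitisation between the arms is also conjecture, because the protocol does not say what makes up the remaining 0.1% of the aloe product. What stands is narrower: the aim speaks of radiation reactions, the endpoint does not, and nothing formal separates the causes.

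**A reader might put a number on the shift.** Assuming that 1–5% of women are sensitised suggests 1–5 percentage points. That rate is not in the protocol. The reading also ignores the 20% and 90% background rates, takes every sensitised woman to react at grade 2 or more, and counts unrecognised allergy that a criterion for known allergy cannot remove. A loss of power built on such rates would need an assumed treatment effect as well, and the protocol states none.

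**The forms and visits give some protection.** This is correct. Nurses see each woman weekly, can describe what they see and can record a decision to stop. But this happens after the exposure has begun.

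**An allergy question may sit in material not shown.** The consent pages were removed and the data-collection CRF appears only as a heading, so ingredients may be disclosed or allergies asked about there. That would lessen the risk, but asking about an allergy does not make it an exclusion. The eligibility lists themselves are shown, and eligibility belongs in the protocol, not in a statistical analysis plan.

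**Inclusion 6 might cover some of these women.** Read generously, its mention of chronic skin disease could take in some histories of contact allergy. It does not say so, and clear skin at entry satisfies its plain wording.

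**Conclusion.** The gap is real. As written, the criteria admit a woman with a known allergy to an ingredient of either gel, and the blinded supply keeps her from identifying it from the package. The main consequence is an avoidable safety exposure. The secondary one is that a contact reaction is graded without formal attribution, which blurs an aim about radiation reactions. That a given contact reaction would be taken for radiation dermatitis is an inference from the forms, not something the protocol states.

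The number of women concerned is probably small and cannot be estimated from the document. No percentage-point shift, loss of power or bias between arms should be claimed. The conclusion rests on the eligibility lists as shown and on no allergy exclusion being stated elsewhere. Severity: minor; a cheap improvement.

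**What to change.** Add one exclusion criterion: *Known allergy or hypersensitivity to hyaluronic acid/sodium hyaluronate, aloe vera, or any preservative or excipient of either study gel.*

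Check it at screening against one combined ingredient list covering both gels, so that neither the woman nor the staff can infer the assignment. The list must name the actual ingredients: the Background section gives one preservative as three names separated by slashes and leaves the rest of the aloe product undescribed.

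The cost is one line in the protocol, one screening question and a few women screened out. The population becomes slightly narrower, against the stated wish for a wide variety of patients. Randomisation, blinding and endpoints are unchanged. The criterion removes recognised allergy only; unrecognised or newly acquired sensitisation will remain.
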